**Patients will discontinue treatment by December 31, 2024, or earlier.**

#### **9.1.2 CTEP IND AGENT #2 (NSC #)**

N/A

#### **9.1.3 AGENT ORDERING**

NCI-supplied agents may be requested by the Principal Investigator (or their authorized designees) at each participating institution. Pharmaceutical Management Branch (PMB) policy requires that the agent be shipped directly to the institution where the patient is to be treated. PMB does not permit the transfer of investigational agents between institutions (unless prior approval from PMB is obtained). The CTEP-assigned protocol number must be used for ordering all CTEP-supplied investigational agents. The responsible investigator at each participating institution must be registered with CTEP, DCTD through an annual submission of FDA form 1572 (Statement of Investigator), Curriculum Vitae, Supplemental Investigator Data Form (IDF), and Financial Disclosure Form (FDF). If there are several participating investigators at one institution, CTEP-supplied investigational agents for the study should be ordered under the name of one lead investigator at that institution.

Agent may be requested by completing a Clinical Drug Request (NIH-986) and faxing it to the Pharmaceutical Management Branch at [contact]. For questions about drug orders, transfers, returns, or accountability call [contact] Monday through Friday between 8:30 am and 4:30 pm (ET) or email [[contact]](mailto:[contact]) anytime.

As of the 8/6/18 amendment, a 6-month supply may be dispensed to patients. When ordering drug with the Pharmaceutical Management Branch (PMB), the Clinical Drug Request (NIH-986) must indicate the request for a 6-month supply. A 6-month supply can only be provided if the PMB has a lot of drug with an expiration date > 6 months.

#### **9.1.4 AGENT ACCOUNTABILITY**

The Investigator, or a responsible party designated by the Investigator, must maintain a careful record of the inventory and disposition of all agents received from DCTD using the NCI Drug Accountability Record Form. See the CTEP web site for Policy and Guidelines for Accountability and Storage of Investigational Drugs (<http://ctep.cancer.gov/requisition/storage.html>).

### **9.2 OTHER INVESTIGATIONAL AGENTS**

N/A

### **9.3 CARBOPLATIN**

#### Availability

Carboplatin is commercially available as a sterile lyophilized powder available in single-dose vials containing 50 mg, 150 mg, or 450 mg of carboplatin. Each vial contains equal parts by weight of carboplatin and mannitol. Commercial supplies of carboplatin will be used for this study. Carboplatin is also available as an aqueous solution in 50 mg/5 mL, 150 mg/15 mL, 450 mg/45 mL and 600 mg/60 mL multidose vials

#### Preparation

Reconstitute lyophilized powder with Sterile Water, 0.9% Sodium Chloride, or 5% Dextrose Injection with volumes of diluents specified below. The reconstituted solution can be further diluted to a concentration as low as 0.5 mg/mL with 0.9% Normal Saline or 5% Dextrose Injection.

Vial Strength	Diluent Volume
50 mg	5 mL
150 mg	15 mL
450 mg	45 mL

#### Storage and Stability

When prepared as directed, the resultant carboplatin solutions, when protected from light, are stable for 8 hours at room temperature. No antibacterial preservative is contained in the formulation, and therefore, it is recommended that carboplatin solutions be discarded 8 hours after dilution.

**NOTE:** Aluminum reacts with carboplatin, causing precipitate formation and loss of potency. Therefore, needles or intravenous sets containing aluminum parts that may come in contact with the drug must not be used for the preparation or administration of carboplatin.

Unopened vials of carboplatin are stable for the life indicated on the package when stored at controlled room temperature (59 - 86°F) and protected from light. When prepared, carboplatin solutions are stable for 8 hours at room temperature. Carboplatin aqueous solution multidose vials maintain microbial, chemical, and physical stability for up to 14 days at 25° C following multiple needle entries.

#### Dosing and Administration

Carboplatin will be administered within one hour after ABT-888 as an intravenous infusion over 30 minutes. Dose calculations are specified in Section 5.1 (Treatment Administration).

## 10 CORRELATIVE/SPECIAL STUDIES

### 10.1 OPTIONAL BLOOD SAMPLES FOR FUTURE GENETIC RESEARCH STUDIES

Optional blood samples will be drawn for future genetic research studies including analysis of possible constitutional determinants of resistance and metabolism of ABT-888. Participants will be requested to provide a blood sample to be stored at ambient temperature for DNA extraction and potential pharmacogenetic analysis. Any genotyping performed will relate to the absorption, distribution, metabolism, elimination or mode of action of study drugs and any comparators, related pathways and other oncogenetic pathways.

### 10.2 MOLECULAR CORRELATES

We will use qualified and validated assay methods (**Table 7**) to assess the relationship between the level of PARP inhibition by ABT-888 and markers of DNA damage in surrogate tissues (PBMC's) and tumor.  $\gamma$ H2AX and RAD51 immunohistochemical assays will be conducted using laser scanning cytometry (LSC) [59, 60]. In preliminary studies, we have shown increased  $\gamma$ H2AX frequency in BRCA-null cells compared to the complemented cells for the PARP inhibitor ABT-888, using scanning laser cytometry (**Figure 4**) that will be used in the clinical trial.

[figure not shown]
**Biomarkers for PARP inhibitors.** The phospho-modified histone  $\gamma$ H2AX serves as a marker for double strand breaks (DSBs); therefore, we will use an antibody (monoclonal mouse Ab from Upstate Biotechnology Anti-phospho-Histone H2A.X (Ser139), clone JBW301) against that protein in immunohistochemical analysis [57]. RAD51 will be loaded onto single-strand regions during HRR that co-stain with the  $\gamma$ H2AX immunostaining, but in BRCA2 cells co-localization should be reduced due to the inability of BRCA2 to function. The number of cells with >10 spots for  $\gamma$ H2AX should indicate the increased formation of DSBs in the presence of ABT-888 and possibly the other PARP inhibitors.

We will also use immunostaining for  $\gamma$ H2AX in hair follicles from eyebrow plucks as a biomarker of pharmacodynamic effect [64, 65].

The recent phase 0 trial in patients with advanced malignancies demonstrated >85% reduction in PAR level in PBMCs after a single oral 25 mg dose [35].

**Table 7 Assays and Biomarkers for patient samples.**

Assay/Biomarker	Sample	Assay	Ref.
PARP Activity	PBMC Tumor	Immunoassay	[61, 62]
$\gamma$ H2AX/RAD51	PBMC Tumor	IHC/LSC	[63-65]
Reversion mutations/ HRR Assay	Tumor (top priority use)	I-Scel EGFP	[50, 66]

**Figure 4** Laser scanning cytometry of wild type (V-79) or BRCA2-null cells (VC-8) exposed to 100 mM for 48 h of the PARP inhibitor ABT-888. Propidium iodide staining of nucleic acids (red) and  $\gamma$ H2AX foci formation (green). Each box represents a different field of a 96-well plate.

### Sample collection.

Sample Collection, Processing and Shipping of PBMCs and fresh-frozen tumor samples are detailed in the National Clinical Target Validation Laboratory (NCTVL) Standard Operating Procedures (in Appendix).

In brief, serial blood samples for PBMC analysis will be collected for all patients according to the following schedule; pre-dose, and 3 hours after ingestion of ABT-888 on Cycle 1, Day 1. In addition, PBMC samples will be obtained 1 to 3 hours after ingestion of ABT-888 on day 1 of cycle 2, and pre-dose and 3 hours post dose on Cycle X (1st cycle after progression when carboplatin is added to the treatment schedule), and 1 to 3 hours after ingestion of ABT-888 on Cycle X + 1 (the second cycle after progression). For the combination arm carboplatin should be administered within one hour after the morning dose of ABT-888 on day 1 of each cycle.

The City of Hope Analytical Pharmacology laboratory will send plasma samples for extraction and analysis of ABT-888 to the Clinical Pharmacology Analytical Facility at the University of Pittsburgh Cancer Institute.

If the patient presents with a biopsiable tumor, then the provision of tumor tissue prior to starting dosing and during treatment with study drugs will be encouraged if clinically appropriate. Optimally, biopsies for comparison will be obtained on day 1 of cycle 1, and day 1 of cycle 2, and at progression (off-study visit). Tumor biopsy will be performed pre-treatment on screening day or pre-treatment on day 1 of cycle 1, and on day 1 of cycle 2 approximately 4-8 h after start of carboplatin (or ingestion of ABT-888 in the single-

agent arm), and then again on the off-study visit. Up to 3 passes will be allowed during each biopsy procedure for obtaining tumor tissue. Samples will be immediately snap-frozen. The top priority will be to analyze for *BRCA* reading frame restoring revertant mutations at baseline and at progression. PAR/ $\gamma$ H2AX/RAD51 assays with the tumor tissue will then be conducted. Since epinephrine can interfere with the PAR assay, the local anesthesia for the tumor biopsy will utilize lidocaine whenever possible and avoid 'lidocaine plus epinephrine'. However, if epinephrine is used, it will be clearly noted in the case report form. Patients will not be excluded from the trial if these samples are not collected.

The complete set of frozen samples will be shipped overnight on dry ice to the following address:

Analytical Pharma. Lab  
City of Hope  
[name]  
[name]  
[name]  
[contact], [name]  
Email: [contact]

All specimens shipped must be accompanied by the Specimen Submission form found in Appendix D. Additionally, a copy of that completed form must be faxed to the Data Coordinating Center at City of Hope, [contact] when specimens are shipped.

*Expected results.* We expect that the  $\gamma$ H2AX will increase as the degree of PARP inhibition increases in PBMC and tumor, but there will be no increase in RAD51 in the tumor due to the absence of *BRCA*. Immunoassay for poly-ADP-ribosylated (PAR) substrates: Abbott Laboratories and the NCI-Frederick laboratories developed and cross-validated a quantitative immunoassay for PAR [61]. The validated assay is a sandwich enzyme chemiluminescence immunoassay employing commercially obtained antibodies to PAR, and pure PAR as a standard. Specimen handling was optimized for both PBMCs and tumor needle biopsies (18 ga), and harmonized for use with the same standards and controls. The validated assay was used to measure PAR levels in PBMCs of healthy donors, in animal models after administration of a single and multiple dosing of ABT-888, and has been used successfully in real time to measure PAR in PBMCs and tumor biopsies in a phase 0 clinical trial [61]. Kits for the CLIA-approved PAR assay will be obtained from the NCI and the research technician performing the PAR assay will be trained at the NCI.

**Determine mechanisms of resistance.** Cells which are *BRCA* null can compensate, in part, for defects in HRR DSB repair by using single-strand annealing and non-homologous end joining (NHEJ) [67]. Patients who receive PARP inhibitors could manifest drug resistance by reconstituting their *BRCA* function. This would lead to

restoration of normal HRR and the therapeutic footing in the original cell type (BRCA null) would be lost, as described in recent reports [50, 51]. Therefore, we will examine *BRCA* sequences from tumor cells from patients treated with ABT-888. The precise germline *BRCA* mutation will be known for all patients.

We anticipate 10-20% (n=8-16) of clinical trial participants will have accessible tumor and consent to biopsy just **prior** to treatment with study drug(s) on the trial. These samples will be used to assess HRR status and whether BRCA expression is restored indicating the presence/absence of reversion mutations prior to initiating our clinical treatments and correlative studies. A proportion of cases are likely to have reversion mutation and/or re-expression of BRCA and restored HRR due to selective pressure from chemotherapy exposure; however, platinum resistance can occur by a non-HRR mechanism so clinical resistance alone does not preclude persistent defective HRR and susceptibility to PARP inhibitors. Approximately 6-12% (n=5-10) may have accessible tumor and consent to biopsy for study **post**-clinical trial.

[figure not shown]
At the close of the protocol, the *BRCA* sequence will be re-determined in available tumor. Full length *BRCA* clones in the pcDNA3.1 expression with a promoter more active in mESCs will be constructed will be modified to introduce any sequence differences from the original *BRCA* sequences. We have the full length cDNA constructs and are constructing the vectors. Point mutations will be introduced into *BRCA* using site-directed mutagenesis, whereas larger deletions or insertions will be constructed using restriction sites. Plasmids hosting the *BRCA1* or *BRCA2* constructs will be transformed into mESCs-DR-GFP that have a GFP reporter for HRR and have either *Brca1*-/- or *Brca2*-/- [69] (**Figure 5**). Those cells have a *GFP* sequence with a homing endonuclease site ISce I that is unique in the *Brca* cells, which are null for one of the 2 *Brca* proteins. Cleavage using the Sce I and HRR reconstitutes the *GFP* coding sequence and allows production of a functional GFP. We will also monitor survival of the complemented and vector only cells to treatment using ABT-888 or ABT-888 and carboplatin. In addition, the reporter assay will be used to determine the fold-increase in GFP fluorescence, as an indicator of HRR in *Brca1*- or *Brca2*-DR-GFP cells [50]. Assays in both these types of cells will analyze both types of revertants. Analysis of *BRCA1* revertants is particularly significant, since it is involved in both HRR and with single-strand annealing (SSA) repair [70]. SSA is postulated to have a role in rescue and restoration of HRR during repair processes [67, 71].

There may be other resistance mechanisms that are involved in *BRCA1* patients, as suggested by Swisher *et al* [70]. DNA repair enzymes such as XPD (Xeroderma Pigmentosum Group D) and ERCC1 (Excision repair cross-complementation group 1) are implicated in the nucleotide excision repair pathway and components of this pathway are thought to be the principal elements in platinum adduct removal. We and others have documented improved outcome after platinum-based chemotherapy associated with decreased ERCC1 expression in lung and breast cancer [72, 73].

In contrast, preclinical data with ABT-888 and irinotecan indicated responsiveness in cell lines with high ERCC1 expression [22], contrary to previous clinical data suggesting that low ERCC1 levels were associated with response to platinum agents in the lung cancer setting [73]. It is conceivable that the concomitant inhibition of PARP1 can overcome ERCC1-mediated resistance to platinum salts, a finding that may be applicable to possible uses of ABT-888 and carboplatin beyond the *BRCA* mutant setting.

The p53-related transcription factor p63 is an essential regulator of mammary epithelial development [25]. It is thought that the p63/p73 network controls platinum agents sensitivity in triple negative BC, and correlates with reduced *BRCA1* expression. *In vivo*, the DNp63 and TAp73 isoforms were co-expressed exclusively in cells with mutant p53. Although it did not discriminate between p63 isoforms, expression detected by immunohistochemistry (IHC) will be used to follow response to treatment [74]. Together with p63, it is possible that p53 status may, in part, mediate response to therapy in *BRCA* carriers, as p53 mutations are prevalent in *BRCA*-associated BC [75], and p53 mutations enhance tumor cell kill by the ABT-888/irinotecan combination in cell lines with high ERCC1 levels [22]. We will assess p53 status (increased expression vs. non-expression) by immunohistochemistry and/or cDNA sequencing (depending on specimen type) using established methods [76, 77].

*Expected results and alternate approaches:* *BRCA* null cells, which were originally derived from germline *BRCA*-mutated cells, and which recover HRR function will potentially manifest resistance to PARP inhibitors and be a potential source of drug resistance. For example, *BRCA2* modifications that develop or are selected for in tumors during therapy may impart resistance to ABT-888 or other PARP inhibitors when the *BRCA2* constructs reflecting patient mutations are transfected into VC8-DR-GFP cells.

**Figure 5. HRR reporter assay using a single copy reporter construct in mammalian cells.** The top construct is a unique insert into genomic DNA that has an I-SceI site disrupting an EGFP sequence. Following introduction of an I-SceI coding sequence, the target site is cleaved and the sequence formed is indicative of the repair mechanism. The easiest type of repair to follow is HRR, which is indicated by GFP signal using FACS (or LSC) analysis. Observation of other modes of recombinational repair can be confirmed using restriction digest and PCR of the region indicated by primers 1 and 2. Adapted from References [64, 66]

Moreover, these transfected cells should also show increased recombination frequencies. We will correlate clinical response with tumor BRCA expression/HRR functional status and ERCC1, p63 and p53 expression via IHC and/or RT-PCR for all participants with available specimens.

We anticipate that the restoration of a BRCA open reading frame will most probably increase HRR function. For the moment, we do not know the percentage of patients who will have restored HRR function, but we expect that a functional HRR system would obviate response to the single agent DNA repair inhibitor treatment arm of the clinical trial described in this proposal. However, we expect that ABT-888 may potentiate carboplatin therapy despite functional HRR. Since it recognizes a relatively proximal (amino-) epitope, a known limitation of IHC with the Ab1 antibody against BRCA1, it is possible we will have difficulty assessing the expression status for more distal truncations or missense mutations. We are currently testing a new monoclonal antibody corresponding to C-terminal amino acids 1839-1863 of Human BRCA1, as well as alternate antibodies for detection of BRCA2 expression, for which no reports, to date, have indicated satisfactory performance in IHC on FFPE. We have lymphoblastoid cell lines for a family with a 15-bp in-frame *BRCA2* mutation, which results in a 5 amino acid loss and is considered deleterious after demonstration of allele specific LOH and tracking/linkage [78]; these should serve as useful reagents to test the systems. We will also test a known acquired intragenic deletion [50] that restores the reading frame and at least partial HRR function in tumor cells that originated from germline *BRCA2* mutant cells. If we have difficulty complementing the mouse Brca cell lines, we will use a BRCA2 deficient human cell line (e.g., CAPAN1) or VC-8 cells available in our laboratory, along with a BRCA2 complemented VC-8 as a control. In the future, we will use a method similar to that recently described using mouse ES cells to analyze unclassified mutants or reversion mutations within mammalian cells [79].

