### **Archival Tumor Collection**

If available, and with the patient's consent, archival tissue specimens should be submitted for molecular correlative studies. Archival tumor block (formalin-fixed paraffin-embedded) from initial breast diagnosis, or other specimen obtained prior to study, should be submitted, along with the corresponding path report, within four weeks of patient registration. If tissue blocks cannot be sent, 8-12 unstained slides may be submitted instead.

Fixed tissues, including paraffin-embedded tumor blocks or formalin-fixed tissues should be sent at ambient temperature. Do not send in the same box as the frozen plasma. Formalin fixed cells should be placed in a sealable bag with absorbent material and placed in an appropriate box or container for the shipping of a potentially hazardous material.

Address shipments to:

Analytical Pharma. Lab  
City of Hope

[name]  
[name]  
[name]  
[contact], [name]  
Email: [[contact]](mailto:[contact])

We anticipate access to formalin fixed paraffin embedded (FFPE) primary tumor tissue specimens for approximately 62 patients of the total 71 possible accrued to the clinical trial. Depending on the specific *BRCA* mutation, we will use IHC to assess *BRCA* protein expression in baseline tumors. We do not expect to identify pre-treatment reversion or resistance since one of the near obligatory steps in development of *BRCA*-associated cancer is the somatic or acquired loss of the wt allele. Subsequent genetic instability could generate reversion mutations in a small subfraction of the samples, but these subfractions are unlikely to be detectable unless subjected to selective pressure.

All specimens shipped must be accompanied by the Specimen Submission form found in Appendix D. Additionally, a copy of that completed form must be faxed to the Data Coordinating Center at City of Hope, [contact] when specimens are shipped.

The Federal guidelines for shipment are as follows:

- a. The specimen must be wrapped in an absorbable material;
- b. The specimen must then be placed in an AIRTIGHT container (like a resealable bag);
- c. Pack the resealable bag and specimen in a styrofoam shipping container;
- d. Pack the styrofoam shipping container in a cardboard box.
- e. The cardboard box must be marked as "BIOHAZARD."

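### The correlation of response with tumor BRCA/HRR status pools archival and entry specimens, although for most participants the available tissue cannot show BRCA status at entry

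*Combined protocol and SAP*

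**What the plan says.** All the relevant text is in Section 10.2 (Molecular Correlates) and Section 14.4.

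- **Analysis set.** Under Expected results and alternate approaches: "We will correlate clinical response with tumor BRCA expression/HRR functional status", and with ERCC1, p63 and p53, by IHC, RT-PCR or both, in every participant who has specimens available. Specimen types are not distinguished.
- **Pre-treatment biopsies.** Under Determine mechanisms of resistance, 10-20% of participants (n=8-16) are expected to be biopsied just before study drug, to see whether BRCA expression has been restored. The stated expectation is: "A proportion of cases are likely to have reversion mutation and/or re-expression of BRCA", with restored HRR, through selection by earlier chemotherapy. Under Sample collection, these biopsies are snap-frozen, and the search for revertant mutations has first priority at baseline and at progression.
- **Archival tissue.** The Archival Tumor Collection subsection asks for fixed blocks "from initial breast diagnosis, or other specimen obtained prior to study". It expects primary-tumor "specimens for approximately 62 patients of the total 71 possible accrued to the clinical trial", treats these as baseline tumors, and will stain them for BRCA protein depending on the patient's mutation. It then says: "We do not expect to identify pre-treatment reversion or resistance". The reason given is loss of the wild-type allele. Small reverted subfractions are called "unlikely to be detectable unless subjected to selective pressure".
- **Antibodies.** The BRCA1 antibody in use binds near the amino end, so distal truncations and missense mutations may be hard to assess; a C-terminal antibody is being tested. Alternate BRCA2 antibodies are also being tested, "for which no reports, to date, have indicated satisfactory performance in IHC on FFPE".
- **Statistics.** Section 14.4 item 3 expects baseline biopsy correlates in about 15 patients and plans logistic regression for response. It does not mention the archival tissue. Section 14.4 calls correlates other than PAR reduction exploratory.

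**The concern.** The hypothesis, stated in Section 10.2, is that a functional HRR system would prevent response to single-agent ABT-888. Testing it needs BRCA/HRR status when ABT-888 starts. A tumor sampled before the chemotherapy that may have selected for reversion gives status at an earlier time. Changing the assay does not help: IHC, RT-PCR or sequencing of an early specimen cannot show a later restoration.

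The two statements about reversion before treatment (likely in a proportion; not expected) are compatible only if the first concerns tumor sampled after chemotherapy and the second concerns archival primaries. Read that way, archival tissue cannot stand in for status at entry, yet the planned correlation places both in one analysis. A finding of no association, reported on some 62 patients, could be taken as evidence against the reversion hypothesis when most of those patients could not inform it. Section 14.4 calls detection of such mutations important for understanding resistance.

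**Working it through.** **Inputs from the documents.** Archival tissue: about 62 of 71. Pre-treatment biopsies: 10-20%, n=8-16 (Section 10.2); about 15 (Section 14.4 item 3). Maximum accrual: 27 lead-in + 44 Phase II = 71.

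**The plan's own biopsy figure.** 10-20% of 71 = 7.1 to 14.2, within two patients of the stated 8-16. Exact agreement needs a total of 80 (8/0.10 = 16/0.20 = 80). The difference is too small to matter here, and the stated 8-16 is used below.

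**Share of patients with archival tissue only.** The plan does not say how many biopsied patients also have a block, so both extremes are shown.

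- Every biopsied patient has a block: (62 - 16)/62 = 46/62 = 74%; (62 - 8)/62 = 54/62 = 87%.
- No overlap, with 8 biopsies: 62/(62 + 8) = 62/70 = 89%. This is possible because 71 - 62 = 9 patients have no block. With 16 biopsies some overlap is unavoidable, and the share falls inside the range.

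The range is therefore 74-89%. Archival coverage itself is 62/71 = 87%.

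**Phase II alone, pro rata.**

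- Archival: 44 x 62/71 = 38.4, or about 38 patients; 22 x 62/71 = 19.2, or about 19 in a full BRCA2 stratum.
- Pre-treatment biopsies: 0.10 x 44 = 4.4 to 0.20 x 44 = 8.8, or about 4-9; in a full stratum of 22, 2.2 to 4.4, or about 2-4.

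**What the biopsies alone can do.** The documents give no prevalence of restoration, so 5-30% is assumed. The chance of seeing at least one restored tumor among f biopsies is 1 - (1 - prevalence)^f:

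| Assumed prevalence | f = 8 | f = 16 |
|---|---|---|
| 5% | 0.34 | 0.56 |
| 10% | 0.57 | 0.81 |
| 20% | 0.83 | 0.97 |
| 30% | 0.94 | about 1.00 |

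So the biopsies may well show restoration. A formal test against response is another matter. Assume response of 0% in restored and 40% in non-restored patients, and Fisher's exact test at 0.05. Power is 0.099 with 5 restored of 16, and 0.004 with 2 restored of 8. An analysis confined to the biopsies is descriptive.

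**The case against.** A reader might infer that the planned correlate cannot show restored BRCA at entry at all. The documents do not support that. The 8-16 biopsies are collected for this purpose, are frozen, and have revertant analysis as first priority, so the fixed-tissue antibody problem is not decisive for them. The correlate also names RT-PCR and HRR functional status besides IHC.

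Nor do the documents say that no BRCA2 antibody works. They say that no satisfactory performance has been reported so far and that alternatives are under test. IHC on archival tissue is already conditional on the mutation, and an archival specimen may be later than the initial diagnosis.

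It is also fair to say that no rule codes archival cases as not restored. The sentence on correlation is a summary covering several markers, and using all specimens is reasonable for ERCC1, p63 and p53. Section 14.4 item 3 counts about 15 biopsies and does not name the archival blocks as predictors.

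Finally, exclusion 3.2.1 rules out most prior platinum and all prior PARP inhibitors apart from iniparib, which may make reversion at entry less common. Up to 27 of the 71 are lead-in patients given the combination, for whom the plan expects that ABT-888 may help despite functional HRR.

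These points rule out an absolute claim and any count of missed cases. They do not supply the missing rule. Nothing in Section 10.2 or 14.4 separates specimens by timing, states which mutations the BRCA1 antibody can resolve, or makes BRCA2 staining on fixed tissue conditional on validation. The exploratory label deals with multiplicity and limited power; it does not correct a predictor measured at the wrong time.

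**Conclusion.** The point holds in a limited form. For most participants (74-89% of those with any specimen) the tissue in the planned correlation cannot show BRCA status at entry; the pre-treatment biopsies can. This rests on the expected 62 blocks and 8-16 biopsies, and on the blocks being largely primary tumor, as the plan describes them. A block taken after the last prior therapy would be informative, which is why specimen dates matter.

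It is tempting to go further and state how many restored patients would be missed, or that the pooled result is biased toward no association by a known amount. Neither can be shown. Section 10.2 says the percentage with restored HRR is unknown, the single-agent hypothesis concerns at most 44 of the 71, and staining error could act in either direction. What can be said is that a null pooled result would be uninterpretable.

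The consequence is small. The correlate is exploratory, has no alpha or power attached, and does not touch the response-rate decision in either stratum.

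**What to change.** Amend the correlation sentence in Section 10.2 and Section 14.4 item 3:

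1. Record the date of each tumor specimen relative to prior therapy.
2. Test restored BRCA/HRR status as a predictor of response only in tissue taken after the last prior therapy, using the revertant sequencing already planned.
3. Report archival BRCA1 expression against response separately, as status at the time of that specimen and only for mutations the antibody can resolve.
4. Use BRCA2 IHC on fixed tissue only once an antibody has been validated.
5. Keep ERCC1, p63 and p53 on all specimens, flagged archival or fresh.

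This needs wording and specimen dates, but no new samples or visits. The cost is a smaller N for the restoration correlate: about 8-16 overall and about 4-9 in Phase II pro rata, plus any archival specimens that prove to post-date the last prior therapy. It should be presented as descriptive.
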